### **3.2.1.c General Treatment Instructions**

- As durable disease stabilization and/or objective tumor response can be seen after early progression before week 12, it is recommended that, in the absence of dose-limiting toxicities (eg, serious immune-mediated adverse reactions), all four doses of nivolumab plus ipilimumab be administered over the initial 12 weeks even in the setting of apparent clinical progression, providing the subject's performance status remains stable.
- All metastatic subjects who enter the induction period, including those who may have discontinued treatment for drug-related AEs and/or who have evidence of clinical progression during the induction period, should obtain a 12-week tumor assessment.
- Based on clinical experience in the ongoing and completed melanoma studies, the following recommendations apply for subject management in light of the week 12 or later tumor assessments:
  - The appearance of new lesions in subjects with other stable or shrinking baseline tumor burden may be experiencing clinical benefit and should continue in follow-up and/or maintenance therapy before alternative anti-cancer agents are considered. These subjects can be seen to have continued tumor shrinkage in follow-up scans.
  - As long as overall tumor burden is stable or decreasing, subjects should remain in follow-up and/or maintenance (see below), even in the presence of new lesions.
  - Clinical progression warranting alternative anti-cancer treatment should be considered only in subjects whose overall tumor burden appears to be substantially increased and/or in subjects whose performance status is decreased.

### **3.4 Follow-up (duration of study)**

- Subjects who are no longer receiving treatment and are removed from the study because of unacceptable toxicity (refractory Grade > 3 immune-mediated adverse reactions) or due to investigator or his designee judgment are managed in follow-up. Efficacy assessments for these subjects during follow-up are as per the standard of care. Date of death is recorded.
- Subjects who discontinue treatments should be followed until death or the closure of the study (whichever is first).

- Subjects who are no longer receiving treatment because of clinical progression or who have switched to alternative treatment are not followed formally except to record the date of death.
- All subjects who come off study for any reason will be followed for at least 60 days, which is equal to 4 half-lives of the longest drug.

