## **1.4 Overall Risk/Benefit Assessment**

There continues to be a significant unmet need for patients with previously untreated, **unresectable or metastatic uveal melanoma**.

Nivolumab monotherapy has demonstrated clinical activity across several tumor types, including advanced prior treated melanoma, with objective response rates of 20 - 41% in 106 melanoma subjects treated at various dose levels in CA209003. Nivolumab has also demonstrated a manageable safety profile. The most common AEs included fatigue, rash, pruritis, diarrhea, and nausea.

The combination of nivolumab and ipilimumab has the potential for increased benefit compared to both ipilimumab monotherapy and nivolumab monotherapy. Preliminary analysis of the evaluable CA209004 subjects revealed that approximately 33% of the subjects had >80% tumor reductions in target lesions by week 12. This compares favorably to < 2% for 3 mg/kg ipilimumab monotherapy based on the CA184020 (N=540) and <3% for nivolumab monotherapy based on the CA209003. However, the combination of nivolumab and ipilimumab also has the potential for increased frequencies of adverse events. The most common (reported at > 10% incidence) treatment related AEs are fatigue, rash, pruritus, diarrhea, lipase increased, pyrexia, ALT increase, AST increased, amylase increased and vitiligo. Although the preliminary data suggests an increase in adverse event frequency of nivolumab combined with ipilimumab compared to ipilimumab monotherapy or nivolumab monotherapy, there were no unexpected adverse events noted in the combination of nivolumab and ipilimumab. In addition, many of the Grade 3-4 adverse events associated with the nivolumab combined with ipilimumab were laboratory in nature, without clinical sequelae and adverse events have been manageable and reversible following intervention dose delays or with systemic steroid treatment.

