## **8.3 Collection and Reporting**

- **All life-threatening or fatal events**, that are unexpected, and related to the study drug, must have a written report submitted within **24 hours** (next working day) of knowledge of the event to the Safety Project Manager in the IND Office.
- **Unless otherwise noted, the electronic SAE application (eSAE) will be utilized for safety reporting to the IND Office and MDACC IRB.**

- **Serious adverse events will be captured from the time of the first protocol-specific intervention, until 100 days after the last dose of drug, unless the participant withdraws consent. Serious adverse events must be followed until clinical recovery is complete and laboratory tests have returned to baseline, progression of the event has stabilized, or there has been acceptable resolution of the event.**
- **Additionally, any serious adverse events that occur after the 100 day time period that are related to the study treatment must be reported to the IND Office. This may include the development of a secondary malignancy.**

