**8.3.1 Serious Adverse Events**

Following the subject’s written consent to participate in the study, all SAEs must be collected, including those thought to be associated with protocol-specified procedures. All SAEs must be collected that occur within 100 days of discontinuation of dosing of the investigational product. If applicable, SAEs must be collected that relate to any later protocol-specified procedure (eg, a follow-up skin biopsy). The investigator should notify BMS of any SAE occurring after this time period that is believed to be related to the investigational product or protocol-specified procedure.

All SAEs whether related or unrelated to the ipilimumab, must be immediately reported to BMS (by the investigator or designee) within 24 hours of becoming aware of the event. If

only limited information is initially available, follow-up reports are required. The original SAE form must be kept on file at the study site.

All SAEs should be faxed or emailed to BMS at:

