### **8.3.4 Nonserious Adverse Events**

The collection of nonserious AE information should begin at initiation of investigational product. If an ongoing nonserious AE worsens in its intensity, or if its relationship to the investigational product changes, a new nonserious AE entry for the event should be completed. Nonserious AEs should be followed to resolution or stabilization, or reported as SAEs if they become serious. Follow-up is also required for nonserious AEs that cause interruption or discontinuation of investigational product, or those that are present at the end of study participation. Subjects with nonserious AEs at study completion should receive post-treatment follow-up as appropriate.

All identified nonserious AEs must be recorded and described in the medical record.

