Baseline local laboratory assessments should be done within 14 days prior to treatment to include: CBC w/differential, LFTs (ALT, AST, total bilirubin, alkaline phosphatase), BUN or serum urea level, creatinine, Ca, Mg, Na, K, Cl, LDH, glucose, amylase, lipase, TSH, Free T4, Free T3, and Hep B and C testing only as clinically indicated (HBV sAg, HCV Ab or HCV RNA). Pregnancy testing for WOCBP (done locally) must be performed within 24 hours prior to the initial administration of study drug at baseline and then within 24 hours of dosing at Week 1 and Week 4 of cycle 1 and , 3 and Week 1 and Week 5 starting from cycle 5 and at the safety follow up visits.

Subjects will be evaluated for safety if they have received any study drug. Toxicity assessments will be continuous during the treatment phase. During the safety follow-up phase, toxicity assessments should be done in person. Once subjects reach the survival follow-up phase either in person or documented telephone calls to assess the subject's status are acceptable.

Adverse events and laboratory values will be graded according to the NCI-CTCAE version 4.0.

On-study weight and ECOG Performance status should be assessed on Day 1 of Weeks 1, 3, 4 and 5 during cycles 1 and 2 (except Cycle 1 Day 1) and Day 1 of Weeks 1, 3 and 5 starting from Cycle 3 and vital signs should be assessed at each on-study visit (except Cycle 1 Day 1). Vital signs should also be taken as per institutional standard of care prior to, during and after dosing. Oxygen saturation by pulse oximetry at rest and after exertion should be assessed at each on-study visit prior to dosing. The start and stop time of the

nivolumab infusion should be documented. Physical examinations are to be performed as clinically indicated. If there are any new or worsening clinically significant changes since the last exam, report changes on the appropriate non-serious or serious adverse event page.

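### Section 3.4 contradicts itself and Section 8 on follow-up after treatment, so collection of serious adverse events to day 100 is not assured in patients who progress or switch therapy

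*Combined protocol and SAP*

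**What the plan says.** Three rules in Section 3.4 apply to a patient who stops for progression.

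- Patients off treatment "because of clinical progression or who have switched to alternative treatment are not followed formally except to record the date of death".
- Everyone who discontinues treatment is to be followed to death or study closure, whichever comes first.
- "All subjects who come off study for any reason will be followed for at least 60 days", a period the plan equates with four half-lives of the longer-lived drug.

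The synopsis gives a fourth: follow-up ends at death or at the start of another treatment.

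Section 8 sets the safety window. Section 8.3 has SAEs captured "until 100 days after the last dose of drug, unless the participant withdraws consent". Section 8.3.1 says: "All SAEs must be collected that occur within 100 days of discontinuation of dosing of the investigational product". Withdrawn consent is the only exception. For non-serious events, Section 8.3.4 gives a start ("The collection of nonserious AE information should begin at initiation of investigational product") but no end date.

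Section 9 adds: "During the safety follow-up phase, toxicity assessments should be done in person". It gives that phase no length and no visit dates. The last column of Table 10 is End of Study. It includes adverse events and laboratory tests, but it is not dated relative to the last dose and nothing is scheduled after it.

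**The concern.** Safety and tolerability is a secondary objective (Section 2.2). An SAE rate to day 100 is interpretable only if someone looks for SAEs to day 100 in every treated patient. Here the duty to collect sits in Section 8, while the follow-up section tells sites not to follow one group formally. A coordinator working from 3.4 and Table 10 would have no scheduled reason to contact a progressor after the exit visit.

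The group matters for two reasons. The general treatment instructions in Section 3 recommend giving all four combination doses even with apparent early progression, so these patients may leave with full induction exposure. They may also receive their next care elsewhere or on another drug, where events are less likely to reach the trial unprompted.

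The missing end date in 8.3.4 adds to this. Section 1.4 notes that "many of the Grade 3-4 adverse events associated with the nivolumab combined with ipilimumab were laboratory in nature". Such events need not meet the seriousness definition in 8.1.1, and so may fall outside the 100-day SAE rule.

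**Working it through.** **1. The plan's 60-day figure.** The half-lives come from Section 1.3.5: ipilimumab 15.4 days, nivolumab 17 to 25 days.

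- Ipilimumab: 4 × 15.4 = 61.6 days, which agrees with 60.
- Nivolumab, the longer-lived drug: 4 × 17 = 68 to 4 × 25 = 100 days, which does not.
- Equivalently, 60 / 25 = 2.4 to 60 / 17 = 3.5 nivolumab half-lives.

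So 60 days fits the shorter-lived drug. This is a side point, but it shows that the 60-day and 100-day periods were not set on one basis.

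**2. Does the 60-day rule reach day 100?** Its starting point is not defined, so I tried three.

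| 60 days counted from | Covered to (day after last dose) | Days uncovered before day 100 |
|---|---|---|
| Last dose | 60 | 100 − 60 = 40 |
| Exit at the week-13 scan, last dose week 10 (21 days earlier) | 21 + 60 = 81 | 100 − 81 = 19 |
| Exit at a maintenance scan, last dose 4 weeks (28 days) earlier | 28 + 60 = 88 | 100 − 88 = 12 |

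The rule reaches day 100 only if exit comes at least 40 days after the last dose. For a patient who exits at the week-13 scan, 100 − 21 = 79 of the 100 days fall after exit.

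**3. Is drug still present in the gap?** Assuming simple exponential decline, the fraction remaining is 0.5^(t / half-life). For nivolumab this gives 0.5^(60/17) = 0.09 to 0.5^(60/25) = 0.19 at day 60, and 0.5^(100/17) = 0.02 to 0.5^(100/25) = 0.06 at day 100. The gap is not drug-free. These fractions are not event rates.

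**4. The rules side by side, for a patient who progresses at week 13.**

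| Source | Duration | Content stated |
|---|---|---|
| 3.4, progression or switch bullet | to death | date of death only |
| 3.4, discontinuation bullet | to death or closure | none |
| 3.4, 60-day bullet | at least 60 days | none |
| Synopsis | to death or other treatment | none |
| 8.3 and 8.3.1 | 100 days | all SAEs |
| 8.3.4 | no end date | non-serious events |
| 9, safety follow-up phase | not stated | in-person toxicity assessment |
| Table 10 | ends at End of Study | adverse events, laboratory tests |

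The first row and the 8.3 row cannot both be carried out as written. No row supplies a dated contact between exit and day 100.

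**5. How large is the group?** The documents give no count of patients expected to stop for progression. The design response rates in Section 9 imply 27 × (1 − 0.20) = 21.6 to 27 × (1 − 0.05) = 25.7 non-responders among 27 evaluable patients. That is only an upper guide, because non-responders include patients with stable disease and patients who stop for toxicity.

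**The case against.** The strongest reply is that Section 8 governs safety, and that the 3.4 bullet only ends scheduled visits and efficacy assessment. Section 8.3 admits one exception, withdrawn consent, and even asks for related SAEs after day 100. Several other places support some follow-up:

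- the 60-day rule covers every reason for leaving;
- Section 6.2.4 documents new and continuing events at early withdrawal;
- Section 6.3.2 reports serious and non-serious events through follow-up visits;
- Section 8.3.4 requires follow-up of non-serious events still present at the end of participation;
- Section 9 monitors laboratory toxicities during follow-up until they resolve, return to baseline or are judged irreversible.

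Much of this stands. A reader might infer that progressors are exempt from adverse-event follow-up, or that laboratory toxicity after their last dose is not collected at all. The documents do not support either reading: they contradict themselves rather than plainly leaving these patients out.

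A reader might also infer that ascertainment is shown to differ by exit reason, because toxicity stops are kept in follow-up. That is not established. Section 3.4 gives toxicity stops no adverse-event schedule either.

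What the reply does not remove is the conflict. The cut-off for switchers appears in both 3.4 and the synopsis, so it is not a stray sentence. The 60-day bullet does not say what is collected. The follow-up visits in 6.3.2 and the safety phase in Section 9 have no dates. A duty to collect SAEs, set against an instruction not to follow formally, leaves the practice to each coordinator's reading.

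**Conclusion.** The point holds as an internal contradiction that should be corrected. If the 3.4 bullet is followed, SAE ascertainment to day 100 is not assured in patients who progress or switch. Any missed events would bias the safety results downward.

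The size that can be stated is a length of time. The 60-day rule leaves 40 of the 100 days uncovered if counted from the last dose, and 19 if counted from exit at the week-13 scan. This assumes that the 60-day follow-up does collect SAEs, which the plan does not say.

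The number of missed events cannot be estimated. A reader might be tempted to multiply an assumed share stopping for progression by an assumed late-event rate and report percentage points. The documents supply neither input, and such a figure would also have to credit the days that the 60-day rule covers. The 100-day window is stated for SAEs only, so the point should not be extended to all immune-mediated events.

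**What to change.** Reconcile the synopsis follow-up entry, Section 3.4, Table 10, Sections 8.3, 8.3.1 and 8.3.4, and the safety text of Section 9. Specifically:

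- State in 3.4 that the plan's own 100-day SAE window applies to every treated patient, whatever the reason for stopping and whether or not new therapy has begun. Align the synopsis.
- Say when the 60-day period starts and what it collects, or remove it if the 100-day window replaces it.
- Add to Table 10 one safety contact for all treated patients at the end of the 100-day window. Make its mode consistent with Section 9, which now asks for in-person assessment in the safety phase and allows telephone only in survival follow-up.
- Record the start date of any new anti-cancer therapy, to support attribution.
- Give an end date for non-serious event collection in 8.3.4.

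These changes concern data collection and leave treatment rules untouched. The cost is amendment wording, one contact per patient, and an attribution judgement for events that arise after a new therapy starts.

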## 4 SUBJECT SELECTION CRITERIA

For entry into the study, the following criteria MUST be met. Any exceptions from the protocol-specific selection criteria must be approved by the Principal Investigator, the IND office medical monitor and/or the Institutional Review Board (IRB) before enrollment.

### 4.1 Inclusion Criteria

1. Willing and able to give written informed consent.
2. History of uveal melanoma and documented metastatic disease with at least one measurable lesion is required defined as  $\geq 1$  cm x 1 cm (on spiral CT or equivalent).
3. Any number of prior therapies is allowed.
4. Required values for initial laboratory tests:
  - WBC  $\geq 2000/uL$
  - ANC  $\geq 1500/uL$
  - Platelets  $\geq 100 \times 10^3/uL$
  - Hemoglobin  $\geq 9$  g/dL
  - Creatinine  $\leq 1.5$  x ULN or creatinine clearance (CrCl)  $\geq 40$  mL/min (using the Cockcroft-Gault formula):
    - Female CrCl =  $(140 - \text{age in years}) \times \text{weight in kg} \times 0.85$   
72 x serum creatinine in mg/dL
    - Male CrCl =  $(140 - \text{age in years}) \times \text{weight in kg} \times 1.00$
  - 72 x serum creatinine in mg/dL AST/ALT  $\leq 3$  x ULN for patients without liver metastasis,  
 $\leq 5$  x ULN for liver metastases
  - Bilirubin  $\leq 1.5$  x ULN, (except patients with Gilbert's Syndrome, who must have a total bilirubin less than 3.0 mg/dL)
5. In suspected patients, no active or chronic infection with HIV, Hepatitis B, or Hepatitis C.
6. Performance status ECOG 0-1.

7. Men and women,  $\geq 18$  years of age. Because no dosing or adverse event data are currently available on the use of ipilimumab in patients  $<18$  years of age, minors are excluded from this study.
8. Baseline imaging in the form of CT chest, abdomen, pelvis with oral and intravenous contrast within 28 days of study entry. For patients with a contrast allergy, choice of alternative body imaging will be at the discretion of the investigator or his designee. MRI of the brain is only needed if clinically indicated.
9. Prior to start of treatment must be more than 21 days elapsed from surgery, radiation therapy, or prior chemotherapy. More than 42 days elapsed from prior immune therapy including vaccines.
10. Women of childbearing potential (WOCBP) and fertile men with partners of childbearing potential must be using an adequate method of contraception to avoid pregnancy throughout the study and for up to 26 weeks after the last dose of investigational product, in such a manner that the risk of pregnancy is minimized.

WOCBP include any female who has experienced menarche and who has not undergone successful surgical sterilization (hysterectomy, bilateral tubal ligation, or bilateral oophorectomy) or is not post-menopausal. Post-menopause is defined as:

- Amenorrhea  $\geq 12$  consecutive months without another cause, or
- For women with irregular menstrual periods and taking hormone replacement therapy (HRT), a documented serum follicle stimulating hormone (FSH) level  $\geq 35$  mIU/mL.

Women who are using oral contraceptives, other hormonal contraceptives (vaginal products, skin patches, or implanted or injectable products), or mechanical products such as an intrauterine device or barrier methods (diaphragm, condoms, spermicides) to prevent pregnancy, or are practicing abstinence or where their partner is sterile (e.g., vasectomy) should be considered to be of childbearing potential.

WOCBP must have a negative serum or urine pregnancy test (minimum sensitivity 25 IU/L or equivalent units of  $\beta$ HCG) within 72 hours before the start of ipilimumab.

Men of fathering potential must be using an adequate method of contraception to avoid conception throughout the study (and for up to 26 weeks after the last dose

of investigational product) in such a manner that the risk of pregnancy is minimized.

Sexually active WOCBP must use an effective method of birth control during the course of the study, in a manner such that the risk of failure is minimized. Before enrolling women of childbearing potential in this clinical trial, investigators must review the guideline about study participation for WOCBP, which can be found in the Good Clinical Practice (GCP) Manual for investigators. The topics include the following:

- general information
- informed consent form
- pregnancy prevention information sheet
- drug interactions with hormonal contraceptives
- contraceptives in current use
- guidelines for the follow-up of a reported pregnancy

Prior to study enrollment, WOCBP must be advised of the importance of avoiding pregnancy during trial participation and the potential risk factors for an unintentional pregnancy. This discussion will be documented on the informed consent form required for study participation.

In addition, all WOCBP or fertile men with partners of childbearing potential should be instructed to contact the investigator immediately if they suspect they or their partner might be pregnant (e.g., missed or late menstrual period) at any time during study participation. If following initiation of study treatment, it is subsequently discovered that a trial patient is pregnant or may have been pregnant at the time of exposure to ipilimumab, including during at least 6 half-lives after product administration, ipilimumab will be permanently discontinued in an appropriate manner. Exceptions to ipilimumab discontinuation may be considered for life-threatening conditions only after consultation with the Medical Monitor or as otherwise specified in this protocol.

Protocol-required procedures for study discontinuation and follow-up must be performed on the patient unless contraindicated by pregnancy (e.g., x-ray studies). Other appropriate pregnancy follow-up procedures should be considered if indicated. In addition, the investigator must report to Bristol-Myers Squibb follow-up information regarding the course of the pregnancy, including perinatal and neonatal outcome. Infants should be followed for a minimum of 8 weeks.

